## **17 APPENDICES**

## **Appendix A    Guidance on contraceptive methods and collection of pregnancy information**

### **DEFINITIONS**

#### **Nonreproductive potential**

1. Premenopausal female with 1 of the following:
  - Documented hysterectomy
  - Documented bilateral salpingectomy
  - Documented bilateral oophorectomy
2. Postmenopausal
  - A postmenopausal state is defined as no menses for 12 months without an alternative medical cause. A high follicle-stimulating hormone (FSH) level in the postmenopausal range may be used to confirm a postmenopausal state in women not using hormonal contraception or hormone replacement therapy (HRT). However, in the absence of 12 months of amenorrhea, a single FSH measurement is insufficient.
  - Females on hormone replacement therapy (HRT) and whose menopausal status is in doubt will be required to use 1 of the highly effective contraception methods if they wish to continue their HRT during the study. Otherwise, they must discontinue HRT to allow confirmation of postmenopausal status before study enrollment.

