## 1.2 STUDY FLOW CHART

	Screening Period		Double-Blind Treatment Period a									Extension		Follow-up a
	Screening	Run-in	3 Random- ization	4	5	6	7	8	9	10	11	12	13	14
Visit	1	2	0 Baseline	1	2	3	4	8	12	18	26	39	52	56
Week	-4	-2	0 Baseline	1	2	3	4	8	12	18	26	39	52	56
Day (window [days])		(±3)	1	7 (±5)	14 (±5)	21(±5)	28 (±5)	56 (±5)	84 (±5)	126 (±5)	182 (±5)	273(±5)	364(±5)	392(±5)
Informed consent	X													
Inclusion criteria	X													
Exclusion criteria	X		X											
Demographics	X													
Medical/Surgical History	X													
Medication History	X													
Body weight, height b	X	X	X	X	X	X	X	X	X	X	X	X	X	X
Vital signs c	X	X	X	X	X	X	X	X	X	X	X	X	X	X
Physical Exam:														
complete	X										X		X	
abbreviated d		X	X			X	X	X	X	X		X		X
Diet & exercise instruction		X	X	X	X	X	X				X		X	
Instruction on basic genito-urinary hygiene & hydration	X	X	X			X	X	X	X	X	X	X	X	
Interactive response technology (IRT) contact e	X	X	X			X	X	X	X	X	X	X	X	X
Randomization			X											
Dispense glucose meter		X												
Collect glucose meter														X
Dispense diary	X	X	X	X	X	X	X	X	X	X	X	X	X	
Collect/review diary		X	X	X	X	X	X	X	X	X	X	X	X	X
Instruction on diabetic ketoacidosis symptoms and glucose testing			X			X	X	X	X	X	X	X	X	
Dispense IMP		X	X				X	X	X	X	X	X		
IMP accounting & compliance			X	X	X	X	X	X	X	X	X	X	X	

Visit	Screening Period		Double-Blind Treatment Period a									Extension		Follow-up a
	Screening	Run-in	3 Randomization	4	5	6	7	8	9	10	11	12	13	14
Week	-4	-2	0 Baseline	1	2	3	4	8	12	18	26	39	52	56
Day (window [days])		(±3)	1	7 (±5)	14 (±5)	21(±5)	28 (±5)	56 (±5)	84 (±5)	126 (±5)	182 (±5)	273(±5)	364(±5)	392(±5)
Concomitant medication	X	X	X	X	X	X	X	X	X	X	X	X	X	X
Self-monitored blood glucose f		X	X			X	X	X	X	X	X	X	X	X
12-lead ECG g		X									X		X	
Laboratory testingh														
FPG	X		X				X	X	X	X	X	X	X	
HbA1c	X		X					X	X	X	X	X	X	
Fructosamine			X				X	X	X	X	X	X	X	
Safety laboratory i	X		X	X	X	X	X	X	X	X	X l	X	X l	X
Cystatin C			X	X	X	X	X		X		X	X	X	X
NT-proBNP			X	X	X	X	X		X		X	X	X	
Fasting lipids			X								X	X	X	
Pregnancy test (WOCBP) j	X		X				X	X	X	X	X	X	X	
FSH and/or estradiol (menopausal women only) j	X													
Sotagliflozin Plasma concentration k							X			X	X l	X	X l	

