- d The abbreviated physical exam should focus on cardiac and respiratory systems, as well as any areas important for assessment of AEs if necessary.
- e Additional visit (recheck creatinine) from visit 8 every 2 weeks, contact IRT for treatment allocation if applicable.
- f Self-monitored blood glucose (SMBG) is to be performed fasting, at least 3 times per week from start of Run-in until end of Treatment Period including on day of each on-site study visit except Visits 4 and 5. Patients will also be requested to self-assess blood glucose levels whenever they experience symptoms of hypoglycemia. SMPG ≤70 mg/dL (3.9 mmol/L) will be documented on the hypoglycemia eCRF. The SMBG will be presented as equivalent self-monitoring plasma glucose (SMPG).
- g The 12-lead ECG recordings should be obtained prior to IMP administration. The ECG will be evaluated as "normal" or "abnormal".
- h All laboratory assessments occur prior to dose of double-blind IMP. All visit dates will be scheduled based on the date of randomization with a ±5 days visit window allowed during the treatment period.
- i Safety laboratory will include hematology and clinical chemistry, please see the list in [Table 2](#). Other clinical chemistry tests will include amylase and lipase.

- j* Serum pregnancy testing only at screening; urine pregnancy testing subsequently. Serum pregnancy test results must be reviewed prior to beginning the Run-in Phase for all women of childbearing potential (WOCBP). Any positive urine test results must be confirmed based on serum pregnancy test. The Investigator may perform additional tests at their discretion or as required by local regulations. For women of nonreproductive potential ([Appendix A](#)), follicle stimulating hormone (FSH) and/or estradiol levels should be tested if the definition of postmenopausal or premenopausal cannot be satisfied, eg, no medical document of hysterectomy or cessation of menses <12 months without an alternative medical cause.

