#### 10.1.1.1.1 On-site Visit 1 (Week -4) Screening Visit

The following procedures/assessments will be performed at Visit 1 (Week -4):

- Obtain the informed consent:
    - The patient will receive verbal information concerning the aims and methods of the study, its constraints and risks, and the study duration. Written information will be provided to the patient. Written informed consent must be signed by the patient and Investigator prior to any investigations
- █ [REDACTED]
- █ [REDACTED]
- Assessment of all inclusion/exclusion criteria
  - Collection of demographic data (age, gender, race, and ethnic origin)
  - Assessment of the patient's medical and surgical history: to include history of T2D, treatment and complications (eye, kidney, history of smoking/tobacco use, history of alcohol, history of amputation events, etc)
  - Complete physical examination including height, body weight
  - Vital signs (SBP, DBP, temperature, HR, and respiratory rate). After 5 minutes resting, seated SBP, DBP, and HR will be assessed 3 times with at least 1 minute between each measurement (See [Appendix C](#) for details).
  - Concomitant medication and medication history, including any prior medications for T2D
  - Instruction on basic genito-urinary (GU) hygiene and hydration (see [Appendix B](#))
  - IRT to be notified (allocation of ID, registration of screening)
  - Patient diary is dispensed and instructions/training are provided

- The following laboratory testing (by the central laboratory):
  - FPG
  - HbA1c
  - Clinical chemistry (including amylase, lipase, and uric acid) and hematology
  - Serum pregnancy testing for WOCBP or serum FSH and estradiol (for women of nonreproductive potential if definition of postmenopausal or premenopausal cannot be satisfied, see [Appendix A](#))
- AEs/SAEs/AESI/EOSI and hypoglycemia (if any) are reported
- Patients are instructed to return to the site in the fasting state for Visit 2 (Week -2).

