#### **Reproductive potential (WOCBP)**

A woman is considered of reproductive potential (WOCBP), ie, fertile, following menarche and until becoming postmenopausal unless permanently sterile. Permanent sterilization methods include hysterectomy, bilateral salpingectomy and bilateral oophorectomy.

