- d The abbreviated physical exam should focus on cardiac and respiratory systems, as well as any areas important for assessment of AEs if necessary.
- e Additional visit (recheck creatinine) from visit 8 every 2 weeks, contact IRT for treatment allocation if applicable.
- f Self-monitored blood glucose (SMBG) is to be performed fasting, at least 3 times per week from start of Run-in until end of Treatment Period including on day of each on-site study visit except Visits 4 and 5. Patients will also be requested to self-assess blood glucose levels whenever they experience symptoms of hypoglycemia. SMPG ≤70 mg/dL (3.9 mmol/L) will be documented on the hypoglycemia e-CRF. The SMBG will be presented as equivalent self-monitoring plasma glucose (SMPG).
- g The 12-lead ECG recordings should be obtained prior to IMP administration. The ECG will be evaluated as "normal" or "abnormal".

Statistical Analysis Plan

Version: Final 3.0

Lexicon Pharmaceuticals Protocol No. EFC15166

Date of Issue: 21 November 2019

Covance Study ID: 000000155203

- h* All laboratory assessments occur prior to dose of double-blind IMP. All visit dates will be scheduled based on the date of randomization with a ± 5 days visit window allowed during the treatment period.
- i* Safety laboratory will include hematology and clinical chemistry, please see the list in Table 2 in protocol. Other clinical chemistry tests will include amylase and lipase.
- j* Serum pregnancy testing only at screening; urine pregnancy testing subsequently. Serum pregnancy test results must be reviewed prior to beginning the Run-in Phase for all women of childbearing potential (WOCBP) unless there is documented history of menopause (based on documented follicle-stimulating hormone [FSH] and estradiol levels – if results not documented then FSH and estradiol will be tested at Screening Visit) or they are surgically sterile. Any positive urine test results must be confirmed based on serum pregnancy test. The Investigator may perform additional tests at their discretion or as required by local regulations.

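### Appendix A and the screening instructions class a woman with less than 12 months of amenorrhoea differently, and nothing says what her FSH/estradiol result is for

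*Protocol*

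**What the plan says.** Protocol Appendix A sets the definitions. On menopause: "A postmenopausal state is defined as no menses for 12 months without an alternative medical cause". FSH may support that conclusion in women not using hormonal contraception or hormone replacement, but "However, in the absence of 12 months of amenorrhea, a single FSH measurement is insufficient". Estradiol is not mentioned. A premenopausal woman counts as nonreproductive only with documented hysterectomy, bilateral salpingectomy or bilateral oophorectomy. For everyone else: "A woman is considered of reproductive potential (WOCBP), ie, fertile, following menarche and until becoming postmenopausal unless permanently sterile".

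The operational sections read differently. Footnote j of the flow chart (Section 1.2) refers to women of nonreproductive potential and says that FSH and/or estradiol should be "tested if the definition of postmenopausal or premenopausal cannot be satisfied, eg, no medical document of hysterectomy or cessation of menses <12 months". Section 9.2.1.3 repeats this. The flow chart row itself is labelled "FSH and/or estradiol (menopausal women only") and is marked once, at Visit 1. The Visit 1 list in Section 10.1.1.1.1 has one combined laboratory item: "Serum pregnancy testing for WOCBP or serum FSH and estradiol (for women of nonreproductive potential if definition of postmenopausal or premenopausal cannot be satisfied").

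The SAP carries its own version of footnote j in Appendix E. There the serum pregnancy test must be reviewed before Run-in for all WOCBP "unless there is documented history of menopause (based on documented follicle-stimulating hormone [FSH] and estradiol levels"), with FSH and estradiol drawn at screening if no results are on file, or unless the woman is surgically sterile.

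**The concern.** The screening instructions describe as nonreproductive a woman who, in their own words, does not satisfy the definition of that class. Under Appendix A the same woman is WOCBP. Sites are then told to draw a hormone sample without being told what a given result means.

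WOCBP status decides several things. It governs the serum pregnancy test at screening, on which E 23 relies, and the urine tests that follow. It also governs the requirement for highly effective contraception through treatment and follow-up, and whether E 24 applies at all. Pregnancy is an adverse event of special interest in Section 10.4.1.3, and the investigational product is to be discontinued if it occurs. With approximately 110 sites planned, different readings are foreseeable. The issue concerns patient safety and consistent application of eligibility criteria. It does not concern the estimation of any treatment effect.

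**Working it through.** No calculation bears on this point. The check follows one case through each place that governs her: a woman with no documented sterilisation, whose menses stopped less than 12 months ago without another medical cause.

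| Place | Class given to her | What is ordered | Effect of the hormone result |
|---|---|---|---|
| Protocol Appendix A | WOCBP: neither postmenopausal nor documented sterile | Highly effective contraception | A single FSH is insufficient; estradiol not mentioned |
| Flow chart rows, Section 1.2 | Not stated; one row is for WOCBP, another for menopausal women only | Pregnancy test at Visits 1, 3 and 7 to 13; hormone test at Visit 1 only | Not stated |
| Flow chart footnote j; Section 9.2.1.3 | Nonreproductive potential, with her situation given as an example | FSH and/or estradiol | Not stated |
| Section 10.1.1.1.1, Visit 1 | Nonreproductive potential, definition not satisfied | Serum pregnancy test *or* FSH and estradiol | Not stated |
| SAP Appendix E, footnote j | Depends on documented menopause, judged on FSH and estradiol | Serum test waived if so documented | Removes the serum test; no 12-month condition |

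Four things follow.

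1. *Class.* Appendix A and footnote j give opposite labels. She cannot be both "following menarche and until becoming postmenopausal unless permanently sterile" and of nonreproductive potential. Footnote j, Section 9.2.1.3 and the Visit 1 list all send the reader to Appendix A, so a site that looks up the definition meets the disagreement directly.

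2. *Test.* The wording in footnote j and Section 9.2.1.3 allows FSH alone, and the flow chart schedules one draw. That is the single measurement Appendix A calls insufficient. The Visit 1 list asks for FSH and estradiol together, on which Appendix A is silent. The tension over the test itself is therefore direct for footnote j and Section 9.2.1.3, and only indirect for Visit 1.

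3. *Relation to the pregnancy test.* In the protocol, only the *or* at Visit 1 presents the hormone test as an alternative to the serum test. The flow chart has two separate rows and footnote j contains no substitution wording.

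4. *Consequence of the result.* No protocol passage gives a hormone result that would move her out of WOCBP, and none says that she stays WOCBP whatever the result.

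Footnote j's other example, a hysterectomy without documents, raises the same question, because Appendix A's nonreproductive list requires documentation.

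**The case against.** The strongest reply is that ordering a test does not contradict a rule that its result is insufficient alone. A site can draw the hormones, apply Appendix A, keep the woman as WOCBP and carry out the pregnancy tests. The protocol's footnote j requires the serum result to be reviewed before Run-in for every WOCBP, and the Visit 1 item still covers anyone who is WOCBP by definition. This stands. A reader might infer that the two sets of rules cannot both be followed; the documents do not support that. They support a narrower statement: the two labels cannot both be right, and the protective reading is open to a site but nowhere stated.

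A reader might also infer that the flow chart orders the hormone test in place of the pregnancy test. It does not.

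It is equally tempting to size the harm as the screening serum test plus eight urine tests missed (Visits 3 and 7 to 13) and 52 + 4 = 56 weeks without required contraception. That follows only if the hormone result takes her out of WOCBP for the whole trial, which no protocol passage says. A count of affected patients would also be guesswork, since the documents give no figure for menopausal status.

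Finally, the SAP copy has limited operational force. Sites work from the protocol, and SAP version 3.0, dated 21 November 2019, reports that the first step analysis had been conducted, which required all patients to have been randomised. Correcting it would not change anyone's screening. It still matters as a further, differing statement of the same rule.

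**Conclusion.** The inconsistency is real and should be corrected. Appendix A makes this woman WOCBP, while footnote j and Section 9.2.1.3 call her nonreproductive. Visit 1 sets the hormone tests against the serum pregnancy test, and the SAP waives that test on hormone levels alone. This is more than missing detail, because the stated instructions conflict and the use of the result is undefined. Sites can therefore reach different answers on pregnancy testing, contraception and E 23/E 24 for the same patient.

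Its size is limited. The number of such women among the 276 planned patients is not given. I judge it probably small, but that is a judgement and not a figure from the documents. No endpoint, analysis or sample-size figure depends on it. The conclusion rests on the wording alone and needs no assumption about how any site actually behaved.

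**What to change.** Reconcile the two flow chart rows and footnote j (Section 1.2), Section 9.2.1.3, the Visit 1 list in Section 10.1.1.1.1, the Appendix A definitions and footnote j of SAP Appendix E. One statement, referred to from the other places, should settle:

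- the class of a woman who does not meet the Appendix A definition, whether because amenorrhoea is shorter than 12 months or because sterilisation is undocumented;
- what the FSH and/or estradiol result is used for, and whether one or both hormones are meant;
- whether the hormone test replaces or accompanies the pregnancy test.

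Which clinical rule applies is for the sponsor's medical team; this point asks only that the passages agree. The cost is wording in a few places in the protocol and one SAP footnote. Both kinds of test are already in the visit schedule.

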#### **Reproductive potential (WOCBP)**

A woman is considered of reproductive potential (WOCBP), ie, fertile, following menarche and until becoming postmenopausal unless permanently sterile. Permanent sterilization methods include hysterectomy, bilateral salpingectomy and bilateral oophorectomy.

### **CONTRACEPTIVE GUIDANCE**

Women of reproductive potential (WOCBP) must use a highly effective method of contraception during the treatment period and the post-treatment follow up period (28 ±3 days). If another contraceptive method is used (such as a barrier method), it should be used in combination with one of the highly effective methods (such as an oral contraceptive).

**Female patients:**

Highly Effective Contraceptive Methods That Are User Dependent
 
Failure rate of <1% per year when used consistently and correctlya

 
• Combined (estrogen- and progestogen-containing ) hormonal contraception associated with inhibition of ovulation 
 
- oral
 
- intravaginal
 
- transdermal
 
 
 

 
• Progestogen-only hormone contraception associated with inhibition of ovulation 
 
- oral
 
- injectable
 
 
 

Highly Effective Methods That Are User Independent

 
• Implantable progestogen-only hormone contraception associated with inhibition of ovulation
 

 
• Intrauterine device (IUD)
 

 
• Intrauterine hormone-releasing system (IUS)
 

 
• Bilateral tubal occlusion
 

 
• Vasectomized partner
 
 
(Vasectomized partner is a highly effective contraceptive method provided that the partner is the sole sexual partner of the woman of childbearing potential and the absence of sperm has been confirmed. If not, an additional highly effective method(s) of contraception should be used. Spermatogenesis cycle is approximately 90 days.)

 
• Sexual abstinence
 
 
(Sexual abstinence is considered a highly effective method only if defined as refraining from heterosexual intercourse during the entire period of risk associated with the study drug. The reliability of sexual abstinence needs to be evaluated in relation to the duration of the study and the preferred and usual lifestyle of the patient.)

NOTE:
 
a Typical use failure rates may differ from those when used consistently and correctly. Use should be consistent with local regulations regarding the use of contraceptive methods for patients participating in clinical studies.

**COLLECTION OF PREGNANCY INFORMATION**

**Male patients with partners of reproductive potential who become pregnant**

- The Investigator will attempt to collect pregnancy information on any female partner of a male study patient who becomes pregnant while participating in this study. This applies only to patients who receive study treatment.

- After obtaining the necessary signed informed consent from the pregnant female partner directly, the Investigator will record pregnancy information on the appropriate form and submit it to the Sponsor within 24 hours of learning of the partner's pregnancy.
- Partner will also be followed to determine the outcome of the pregnancy. Information on the status of the mother and child will be forwarded to the Sponsor.
- Generally, follow-up will be no longer than 6 to 8 weeks following the estimated delivery date. Any termination of the pregnancy will be reported regardless of fetal status (presence or absence of anomalies) or indication for procedure.

### **Female patients who become pregnant**

- The Investigator will collect pregnancy information on any female patient, who becomes pregnant while participating in this study.
- Information will be recorded on the appropriate form and submitted to the Sponsor within 24 hours of learning of a participant's pregnancy.
- Participant will be followed to determine the outcome of the pregnancy. The Investigator will collect follow-up information on participant and neonate, which will be forwarded to the Sponsor. Generally, follow-up will not be required for longer than 6 to 8 weeks beyond the estimated delivery date.
- Any termination of pregnancy will be reported, regardless of fetal status (presence or absence of anomalies) or indication for procedure.
- While pregnancy itself is not considered to be an AE or SAE, any pregnancy complication or elective termination of a pregnancy will be reported as an AE or SAE.
- A spontaneous abortion is always considered to be an SAE and will be reported as such.
- Any SAE occurring as a result of a post-study pregnancy which is considered reasonably related to the study treatment by the Investigator, will be reported to the Sponsor as described in [Section 10.4.3](#). While the Investigator is not obligated to actively seek this information in former study patients, he or she may learn of an SAE through spontaneous reporting.

## **Appendix B Recommendations on basic genito-urinary hygiene, maintaining hydration and recognizing diabetic ketoacidosis**

Patients with T2D are at risk for developing genito-urinary (GU) infections. The following guidelines should be communicated to females and uncircumcised males regarding GU infections. Patient communication cards will be printed with the following:

For females:

“The following advice may be useful in helping you to keep your bladder and urethra free from infection:

- Go to the toilet as soon as you feel the need to urinate, rather than holding it in.
- Wipe from front to back after going to the toilet.
- Practice good hygiene by washing your genitals every day, and before having sex.
- Empty your bladder after having sex.”

For uncircumcised males:

“The following advice may be useful in helping you to keep the foreskin free from infection:

- Wash the end of your penis and foreskin with soap and water (do not let soap get in the opening).
- After your shower or bath, dry the end of your penis and foreskin properly and replace the foreskin.
- Also, when you urinate, slide the foreskin back enough so that urine does not get on the foreskin-this helps to keep it clean.”

